11.2 Ordinal Scale of Clinical Improvement

Since there are 9 categories of the WHO Ordinal Scale of Clinical Improvement and these categories are ordinal in nature (higher score correlates to a higher severity level) it is possible to analyze this endpoint as a continuous scale variable.

The mean change in the WHO Ordinal Scale of Clinical Improvement at each timepoint will be compared between treatment groups using a mixed model with repeated measures (MMRM), with baseline score and weighted COVID severity risk score as covariates. Due to the small sample size and unknown variances for the two independent treatment groups, a test for equal variances and normality will be applied prior to choosing the inferential

statistical method to employ. If the test for equal variances and normality is > 0.10 (indicating that the variances are not significantly different and the data is close to normally distributed) the parametric MMRM will be used to test for treatment group differences. If the test for equal variances or normality is ≤ 0.10 (indicating that the variances are significantly different, or the data is non-normally distributed) then a non-parametric MMRM will be used.

The model will test the null hypothesis that the differences in least-square (LS) means between the active and placebo groups over 90 days is equal to zero. LS means will be estimated at each visit along with treatment differences, p-values, 95% confidence intervals for the difference in LS means, and an effect size based upon Cohen's D will be provided for treatment comparisons.

11.3 Time to Clinical Improvement on the Ordinal Scale of Improvement

Time to a clinical improvement (days) will be defined as an improvement in the WHO Ordinal Scale of Clinical Improvement of at least one category (i.e., a 1-point improvement, decrease) from baseline. For example, a 6 at baseline to 5 would constitute an improvement.

Subjects that achieve a clinical improvement will be summarized by number and percentage and analyzed for treatment group differences by use of Barnard's test.

For subjects that did reach a clinical improvement, the time taken to reach a clinical improvement will be analyzed with a Cox PH model with descriptive statistics provided by a Kaplan-Meier analysis, including median time to event, and log-rank test as described above.

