3.2 Study Endpoints

- All-cause mortality.
- Ordinal Scale of Clinical Improvement, absolute values and changes from start of treatment to Days 2, 3, 7, 15, and 30.
- Time to a 1-point decrease on the Ordinal Scale of Clinical Improvement from start of treatment.

- Area under the severity versus time curve, where severity is defined by the Ordinal Scale of Clinical Improvement and time is measured from start of treatment to Days 2, 3, 7, 15, and 30.
- Days of supplemental oxygen or mechanical ventilation from start of treatment (up to 90 days).
- First Intensive Care Unit (ICU) discharge
- Days in ICU from start of treatment (up to 90 days).
- Discharge from hospital.
- Days hospitalized from start of treatment (up to 90 days).
- Severity of ARDS as defined by the Berlin criteria, absolute values and changes from start of treatment to Days 2, 3, 7, 15, and 30.
- Cytokine and biomarker results, absolute values and changes from start of treatment to Days 2, 3, 7, 15, and 30.
- Adverse events (AEs) and serious adverse events (SAEs) within 90 days from start of treatment.

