6. DEFINITIONS OF SUBJECT POPULATIONS TO BE ANALYZED

- Modified Intent-to-Treat (mITT) and Safety analysis set: All enrolled subjects who were randomized and received at least 1 dose of randomized investigational product, CAP-1002 or placebo.

Note that the “as-treated” principle will be applied to all evaluations;(i.e., participants who receive a treatment other than the one assigned in the randomization list will be analyzed as belonging to the actual treatment group and not that assigned by randomization).

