11. EFFICACY ANALYSIS

The modified Intent-to-Treat Population (as Treated) is defined as all enrolled and randomized subjects who received any amount of study treatment; the mITT population will be utilized for all efficacy analyses. All summary tables will be displayed by treatment arm.

This is a Phase 2 proof of concept study, so a hierarchical testing order will be specified, but p-values will be utilized for descriptive purposes even if a step in the hierarchy is not met and there will be no adjustment for multiplicity of analyses. In addition to the analysis by severity of COVID risk at baseline, additional subgroup analyses will be conducted on an ad-hoc basis and will be fully described in the clinical study report.

The primary analysis for each efficacy endpoint will be as follows, unless otherwise noted in the corresponding section. A Cox Proportional Hazards (PH) model will be utilized to characterize overall survival or time-to-event, correcting for baseline COVID severity risk score. This risk score will be calculated based on historical data and will include baseline characteristics of age, weight, sex, and presence of comorbidities. In addition, unadjusted Kaplan-Meier curves will be presented by treatment group and summary statistics will include estimates of median survival (and corresponding 95% confidence interval), minimum and maximum time, and the number of censored subjects. The overall survival time will be compared between the treatment arms using a log-rank test.

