11.1 All-Cause Mortality

Survival will be measured as the time (days) between the date of the start of treatment and the date of death. For subjects not known to be deceased at time of analysis, the time between date of start of treatment and date of last contact or date lost to follow-up will be calculated and used as a censored observation in the analysis. If this date is after the data cut-off, subjects will be censored at the date of data cut-off. The final cutoff for the survival analysis will be as long as possible, and a calendar date for cutoff will be determined prior to final unblinding of the study.

The Death Report (dataset: DR) will be utilized to capture the survival information (date of death).

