11.7 Days in ICU and Time to Discharge

Duration in the ICU (days) will be defined in two ways:

- (1) The interval from the subject’s date/time of ICU admission to the date/time the subject is discharged from the ICU (Hospitalization dataset: AEHO). If a subject is admitted to the ICU multiple times, then all ICU visits will be added together to calculate the duration in ICU.
- (2) The interval from the subject’s date/time of ICU admission after study drug administration to the date/time the subject is discharged from the ICU (Hospitalization dataset: AEHO). If a subject was admitted to the ICU multiple times, then all ICU visits will be added together to calculate the duration in ICU.

Those subjects that were not admitted to the ICU or have no documentation of being discharged from the ICU will be censored for time to event analysis and will be imputed as the highest or lowest score for purposes of continuous outcome analysis.

The following censoring/ imputation rules will be followed:

- (1) If subjects do not have a documented admittance into the ICU, the duration in ICU will be censored at Day 1, or an imputed score of zero.
- (2) If subjects are in ICU through the entire follow-up phase, then the duration in ICU will be censored at the end of study date (maximum of 90 days), or imputed as the days in the study.
- (3) If subjects die while in ICU, then the duration in ICU will be censored at the date of death, or imputed as the days until death.
- (4) If subjects withdraw from study (any reason) while in the ICU, then duration in ICU will be censored at the date of study withdrawal or imputed as the number of days until withdrawal.
- (5) If subjects are in ICU at the time of database lock and analysis (unlikely, but possible), the duration in ICU will be censored on the date of database lock or imputed as the number of days until database lock.

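### SAP 11.3 analyses time to clinical improvement only in subjects who improved, so its hazard ratio and median do not compare the treated arms

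*SAP*

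**What the plan says.** SAP 3.2 lists the endpoint as "Time to a 1-point decrease on the Ordinal Scale of Clinical Improvement from start of treatment", with no restriction to subjects who improve.

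SAP 11.3 analyses it in two parts. The proportion improving is compared with Barnard's test. The timing is then handled as follows: "For subjects that did reach a clinical improvement, the time taken to reach a clinical improvement will be analyzed with a Cox PH model", with a Kaplan-Meier median and a "log-rank test as described above". Section 11.3 gives no censoring rule.

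The text above it is the general template in SAP 11. There, "the mITT population will be utilized for all efficacy analyses", and the Kaplan-Meier output includes "minimum and maximum time, and the number of censored subjects". SAP 6 defines mITT as everyone randomised and dosed, analysed as treated ("participants who receive a treatment other than the one assigned in the randomization list will be analyzed as belonging to the actual treatment group"). SAP 9.4.3 keeps withdrawn subjects in every analysis up to the time they withdraw.

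For other endpoints, the SAP generally censors subjects without the event. In 11.1 the follow-up of subjects not known to have died "will be calculated and used as a censored observation in the analysis". In 11.7, subjects who "have no documentation of being discharged from the ICU will be censored for time to event analysis". Section 11.9 does the same for hospital discharge.

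**The concern.** Whether a subject improves is an outcome of treatment. If CAP-1002 changes who improves, restricting the timing analysis to improvers compares two differently selected groups. The hazard ratio and median then answer a different question from the endpoint in SAP 3.2. What is lost is the comparison of all treated subjects. Because mITT is as-treated, that is not strictly the comparison of the randomised groups.

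The restriction also fits badly with the template it borrows. Among improvers the censored count is zero by construction, so that output would carry no information. A subject who withdraws unimproved contributes nothing, contrary to SAP 9.4.3.

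The qualifier in SAP 11 that lets a section depart from the default belongs to the sentence on the method of analysis. The mITT sentence carries no exception.

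SAP 9.3 will weigh the totality of evidence for proof of concept. A hazard ratio of the wrong sign would mislead that judgement whatever status its p-value has.

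**Working it through.** The plan gives no improvement rate, effect size or power for this endpoint, so there is no figure of its own to reproduce. Taken from the documents: about 30 treated per arm (SAP 4), 1:1 allocation, and ordinal scores at Days 2, 3, 7, 15, 30, 60 and 90. Assumed: all rates and times, and two-sided 0.05. The risk-score covariate is left out because the SAP does not define it numerically. Hazard ratios (HR) above 1 favour CAP-1002.

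**Hand example.** Let 27/30 improve on CAP-1002 and 18/30 on placebo, with one third of improvers in each arm at Days 3, 7 and 15 (2, 6 and 14 days from Day 1). Timing among improvers is identical. At each event time, with d events and n1 CAP-1002 subjects among N at risk, the log-rank expected count is E = d·n1/N and the variance is V = d·(n1/N)·(1 − n1/N)·(N − d)/(N − 1).

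*All mITT, 15 non-improvers censored:*
- 2 days: n1/N = 30/60, d = 15, E = 7.5, V = 2.860
- 6 days: n1/N = 21/45, d = 15, E = 7.0, V = 2.545
- 14 days: n1/N = 12/30, d = 15, E = 6.0, V = 1.862

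Observed 27, expected 20.5, variance 7.268. Chi-square = 6.5²/7.268 = 5.81, p = 0.016. The Cox HR (Efron ties) is 2.12 (95% CI 1.16 to 3.88). Medians are 6 days on CAP-1002 (18/30 improved by then) and 14 on placebo (12/30 by 6 days, 18/30 by 14).

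*Improvers only (45 subjects, none censored):* n1/N is 27/45, 18/30 and 9/15, so E = 9 each time. Observed 27, expected 27, p = 1.00, HR 1.00 (0.55 to 1.82), medians 6 and 6.

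On the same data Barnard's p is 0.0076. The trial would therefore report a difference in proportions beside an HR of exactly 1.

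**Simulation.** 6,000 trials per row except the row marked *; Monte Carlo standard error is at most √(0.25/6000) = 0.65 points. Improvement times are moved up to the next visit, and nobody is lost to follow-up. Improvers' times are exponential with median 7 days unless stated. HRs are geometric means.

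| Assumption (placebo vs CAP-1002) | HR, all mITT | HR, improvers | Log-rank rejection, all vs improvers |
|---|---|---|---|
| 50% vs 75% improve, equal speed | 1.92 | 0.98 | 49% vs 5% (Barnard 51%) |
| 80% vs 90%, equal speed* | 1.32 | 1.00 | 16% vs 6% (Barnard 17%) |
| 60% vs 85%, extra improvers at Day 30 or 60 | 1.60 | 0.60 | improvers: significant against the drug in 36% |
| 60% vs 85%, extra improvers at Day 15 or 30 | 1.73 | 0.83 | improvers: significant against the drug in 12% |
| Harm: 85% vs 60%, drug loses the late improvers | 0.63 | 1.67 | improvers: significant for the drug in 36% |
| 85% in each arm, median 10 vs 5 days | 1.37 | 1.92 | 22% vs 61% (Barnard 4%) |
| 70% in each arm, median 10 vs 5 days | 1.23 | 1.94 | 11% vs 53% |
| 50% vs 75%, median 10 vs 5 days | 2.26 | 1.90 | 69% vs 46% |
| True HR 2, placebo rate 0.02/day, no deaths | 1.98 | 1.50 | 69% vs 34% (Barnard 43%) |
| Null: 60% in each arm | about 1 | about 1 | 5.7% vs 5.0% |

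A second null, with improvement 0.05/day and death 0.0125/day in both arms, rejects in 5.0% either way.

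**Death before improvement is a separate question.** Suppose the drug only lowers death before improvement, from 0.025 to 0.005 per day, with improvement at 0.05 per day in both arms. The HR then depends on the rule:

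| An improvement counts if | All mITT, deaths kept at risk to Day 90 | All mITT, censored at death | Improvers only |
|---|---|---|---|
| it precedes death | 1.65 | 0.93 | 0.75 |
| the subject also survives to the visit that scores it | 1.84 | 0.99 | 0.68 |

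Correcting the population moves 0.75 to 0.93 (or 0.68 to 0.99). The rest comes from the death rule. Neither rule has more power throughout: with equal deaths at 0.0125/day, placebo improvement 0.05/day and true HR 2, power is 43% kept at risk, 63% censored at death and 47% in improvers.

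**The case against.** The strongest reply is that this is loose drafting. Section 11.3 points back to the general template, which counts censored subjects, so ordinary censoring may have been intended. That is possible, but the sentence as written tells a programmer to drop non-improvers, and two programmers could fairly produce different hazard ratios.

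The rules in 11.1, 11.7 and 11.9 belong to other endpoints. They show the SAP's usual practice and do not bind 11.3, which omits a rule. Censoring subjects never admitted at Day 1 (11.7, 11.9) in effect removes them too, so the practice is not uniform. This stands. The conflict rests on the mITT sentence and censored count in SAP 11, the endpoint in 3.2, and 9.4.3.

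The larger scenarios may be pessimistic. Intubated patients are excluded, and a subject discharged with a score of 0 to 2 has improved on any in-hospital baseline, so a Day 90 non-improver is mostly someone who died or stayed in hospital. At 80% vs 90% the gap shrinks to 1.32 against 1.00. In both equal-speed rows Barnard's test rejects about as often as the all-mITT log-rank. There, what is lost is a valid hazard ratio and median, not a test. This also stands, but it does not cover the reversal and enlargement rows, where the improver result is misleading in itself.

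**Conclusion.** The concern holds for the text as written. The improvers-only analysis conflicts with the SAP's own population rule and endpoint, and its hazard ratio and median do not describe the treated arms. Depending on how the drug acts, the error can hide a difference (1.92 becomes 0.98), reverse it (1.60 becomes 0.60, or 0.63 becomes 1.67 for a harmful drug) or enlarge it (1.37 becomes 1.92). The direction cannot be known in advance. Every size rests on assumed rates and an unadjusted model. If improvement rates and timing are the same in both arms, there is no distortion.

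The consequence is moderate. The endpoint is one of 12 exploratory ones, p-values are descriptive, and the MMRM (11.2) and AUC (11.4) analyses of the same scale are not restricted to improvers. It should be fixed before unblinding, but it does not undermine the trial.

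**What to change.** **Population.** Replace the restriction in 11.3 with: all mITT subjects are included, with time measured from start of treatment; subjects alive without improvement are censored at their last ordinal assessment, no later than the Day 90 visit. Apply the Cox model, log-rank test and median to that set. Keep Barnard's test. Time among improvers may be described without a treatment test.

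**Deaths.** State the rule as a separate choice. One option keeps subjects who die unimproved in the risk set as not improved through Day 90 and labels the result a subdistribution-type hazard ratio. Define that end as a day count, since a dead subject has no Day 90 visit and the visit window is ±7 days. This option differs from the censoring at death in 11.7 and 11.9, so the SAP should say so. If censoring at death is preferred, state that instead.

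**Cost.** Two short statements and no new data: the scale is scheduled to Day 90 and death dates are captured. There are two downsides. Under the first death option this hazard ratio reads differently from those in 11.7 and 11.9. And if the drug only speeds improvement in subjects who would improve anyway, the all-mITT log-rank has less power (22% against 61% at 85% improving per arm).

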 Follow-up phase will be conducted on Days 2, 3, 7 (± 1 day), 15 (± 1 day), 30 (± 3 days), 60 (± 3 days) and 90 (± 7 days). Follow-up will either be conducted in the inpatient setting or as a phone follow-up should the subject be discharged. Note that as long as the subject remains hospitalized on study the safety of the subject will be monitored on a daily basis per standard of care.

 Data that will collected on a subject-by-subject basis based on occurrence during study participation.

 Prior to baseline assessments on Day 1, Investigator is required to confirm the subject's eligibility based on the inclusion and exclusion criteria in [Section 5.1](#) and [Section 5.2](#).

 Assessment to occur prior to infusion on Day 1.

 Assessment will be conducted in the inpatient setting only if the subject is still hospitalized for this visit.

 Every 15 minutes from pre-infusion through 2 hours post-infusion.

 To capture type of ventilator and respiratory support (e.g., endotracheal ventilator, nasal O2 cannula, face mask, or ECMO) and twice daily SpO2 (%), FiO2 (%) and respiration rate (bpm).

 On treatment day, include immediately pre- and post-infusion.

 Only to be conducted for women of childbearing potential.

 Includes the following clinical laboratory samples: CBC, CMP, CRP, cytokine assay (IL-1, IL-6, TNF- $\alpha$ , INF- $\gamma$ , IL-10), troponin I, myoglobin, ferritin, and procalcitonin.

 Blood samples will be taken and submitted to a central laboratory for future proteomic assay assessment. Information on the assay and procedures for collection and shipping are located in the laboratory manual.

 Subjects will be randomized approximately 1 to 5 days prior to the planned infusion in Treatment Phase to allow enough time for IP ordering and delivery.

-  IP will be ordered approximately 1 to 5 days prior to the infusion (Day 1) in Treatment Phase to allow for enough time for IP delivery. Please see the IP Manual for ordering instructions and timelines.
-  Subjects will be observed for at least 2 hours post-infusion, including vital signs assessments every 15 minutes. The clinical site will observe local institutional policies related to parenteral infusions and post-infusion monitoring. A site Investigator will assess the subject for AEs.

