Assessments to evaluate efficacy will be performed at trial visits as indicated in Schedule of Activities ([Section 1.3](#)).

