2. OVERVIEW OF STUDY DESIGN

Experimental Design:

This is a randomized, double-blind, placebo-controlled, pilot, Phase 2 exploratory study that will enroll subjects with a clinical diagnosis of COVID-19 confirmed by laboratory testing and who are in severe or critical condition as indicated by life-support measures.

Up to 60 subjects will be enrolled in the study. Eligible subjects will be randomized to either the CAP-1002 or placebo group (1:1 ratio) and undergo baseline safety and efficacy assessments approximately 1 to 5 days prior to the administration of investigational product (IP). Treatment administration consists of 1 peripheral intravenous (IV) infusions of IP [REDACTED] [REDACTED] for a total of 150M CDCs or matching placebo) administered at the clinical site.

Subjects will receive 1 administration of IP on study Day 1. Background standard of care treatment and practices will be maintained for all patients enrolled in the study.

[figure not shown]
There is no planned dose adjustment. Should an acute toxicity arise during the infusion (i.e., hypersensitivity reaction or pulmonary decompensation), the infusion should be terminated immediately, and the actual total dose administered recorded. Any decision about re-challenging should be made after discussions with the Investigator, Medical Monitor, and other medical experts who may be required to make an informed decision.

Subjects will complete Screening followed by a Treatment and Follow-up phase. A detailed medical history will be collected, including the presence of any co-morbidities and risk factors believed to be associated with COVID-19 outcomes (i.e., age, gender, diabetes, chronic obstructive pulmonary disease [COPD] or respiratory conditions, body mass index, cardiovascular or renal disease) or emergent factors since the time of infection. Screening and randomization will be conducted approximately 1 to 5 days prior to IP administration to allow enough time for IP delivery to the clinical site. Eligibility must be reviewed and confirmed on Day 1 prior to the infusion of IP. Follow-up will be conducted on Days 2, 3, 7, 15, 30, 60, and 90 either in the inpatient setting or by telephone if the subject has been discharged.

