4. SAMPLE SIZE

Up to a total of 60 subjects (approximately 30 in each group, CAP-1002 and placebo) will be enrolled and treated in this study. Subjects who are enrolled and randomized but not treated for whatever reason will be replaced for a total sample size of 60 treated subjects. Adequate information is not currently available for formal sample size calculations for this study. The proposed study size reflects a reasonable estimate of subject numbers to support descriptive and correlative assessments involving clinical safety and efficacy information to support further clinical studies.

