5. RANDOMIZATION, BLINDING, AND REPLACEMENT OF SUBJECTS

Subjects who meet all enrollment criteria will be randomized to receive either CAP-1002 or placebo (1:1 ratio). Only personnel who have been delegated by the Principal Investigator to randomize subjects may complete the task. Subjects will be randomized in the EDC system approximately 1 to 5 days in advance of their first administration. This lead time is to ensure adequate IP shipping time (see IP Manual for shipping specifications). The master randomization list will be generated per the study Randomization Plan and Specifications in

SAS or comparable software and held in confidence by the unblinded programmer preparing the master randomization list.

This is a double-blind, placebo-controlled trial. Investigational product will be prepared for IV infusion by site personnel who have been appropriately delegated by the Principal Investigator. The IP syringes, once prepared, will appear identical for both treatment groups. However, an investigational pharmacist may be able to differentiate CAP-1002 from placebo on the basis of the opacity of the thawed concentrate observed during IP preparation. For this reason, the investigational pharmacists will have limited interaction with the blinded investigative site personnel.

Site personnel and subjects, staff members at clinical research organizations (CROs), and Capricor personnel will remain blinded to treatment assignment throughout trial conduct. An unblinded DSMB, unblinded statistician, and the DSMB administrator will remain firewalled from any blinded individual involved in trial conduct, services, and/or oversight.

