13.3 Testing/Validation Plan and Software System

Statistical Analysis Software (SAS) version 9.4 or later will be used to analyze the data, create summary tables, subject data listings, and graphical representation of the data. All SAS computer programs will be validated using industry standard validation procedures including independent quality control programming.

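### SAP 11.3 fits a continuous-time Cox model to heavily tied visit-day data and names no tie method; if Breslow ties were used, a true hazard ratio of 2.0 would be estimated at about 1.6 to 1.75 on nominal visit days

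*SAP*

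**What the plan says.** **Endpoint and model.** SAP 11.3 defines improvement as a fall of at least one category from baseline and states that "the time taken to reach a clinical improvement will be analyzed with a Cox PH model with descriptive statistics provided by a Kaplan-Meier analysis", with a log-rank test. The sentence opens by restricting this analysis to subjects who did improve. SAP 11 makes a Cox model, adjusted for a baseline severity risk score, the primary analysis of each efficacy endpoint unless the endpoint's own section says otherwise. Section 11.3 does not. The Kaplan-Meier curves are described there as unadjusted, and p-values as descriptive.

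**When the score is taken.** Protocol 8.1: "Assessments to evaluate efficacy will be performed at trial visits as indicated in Schedule of Activities". SAP 2: "Follow-up will be conducted on Days 2, 3, 7, 15, 30, 60, and 90". The schedule tables list the ordinal scale at screening, on Day 1 before infusion, and at those seven follow-up visits. The third footnote to Protocol 1.3 adds windows: "Follow-up phase will be conducted on Days 2, 3, 7 (± 1 day), 15 (± 1 day), 30 (± 3 days"), then ±3 days for Day 60 and ±7 days for Day 90. Days 2 and 3 have none.

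**What is not said.** No section names a tie method, a grouped-time or interval-censored model, or the date to assign to an improvement that happens between visits. SAP 8.6 applies nominal visit labels to summary tables, and SAP 9 leaves unscheduled data to the listings. On software, SAP 13.3 says only: "Statistical Analysis Software (SAS) version 9.4 or later will be used to analyze the data".

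**The concern.** A continuous-time Cox model assumes that few subjects share an event time. Here the gaps between later visits are 8, 15, 30 and 30 days, so large groups of subjects are recorded as improving together. The partial likelihood then has to be approximated, and the approximations differ when ties are this heavy. An identical visit grid in both arms does not cancel the effect, because Breslow's method pulls the hazard ratio towards 1 in any case.

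The SAP presents the trial as a proof of concept that should inform further studies, so the estimate is the main product of this analysis. As written, a program option that the SAP leaves open can move it materially. The adjusted Cox result and the log-rank result on the same data could also disagree for a purely technical reason.

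**Working it through.** **Inputs from the documents.** "Up to a total of 60 subjects (approximately 30 in each group, CAP-1002 and placebo) will be enrolled and treated in this study" (SAP 4); 1:1 allocation (SAP 5); seven post-baseline visits with the windows above. The plan states no power, event count or hazard ratio, so it has no figure to reproduce.

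**Assumptions.** True hazard ratio 2.0 (1.0 and 1.5 also run); exponential times; control median 4, 7, 14 or 30 days with dropout of 0.02, 0.015, 0.01 or 0.005 per day respectively; two-sided 0.05, Wald tests for the Cox and log-log models. The severity risk score is left out.

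**1. Why Breslow shrinks the estimate.** At a visit where d of n subjects at risk improve, with n₁ and n₀ at risk per arm, Breslow's score at a hazard ratio of 1 is d₁ − d·n₁/n. This is the log-rank numerator. Breslow's information is d·n₁n₀/n², while the log-rank variance is that times (n − d)/(n − 1). Breslow therefore overstates the information by (n − 1)/(n − d). The largest ties in the simulations held 13 to 20 events. With the largest possible risk set, 60, the factor is 59/47 = 1.26 for 13 events and 59/40 = 1.48 for 20, and it is larger with fewer at risk. The log hazard ratio shrinks roughly by this factor and the z statistic by its square root. Efron's method depletes the risk set within each tie and avoids most of this. The log-rank test uses the smaller variance directly.

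**2. Benchmark.** Schoenfeld: power = Φ(√(d/4)·ln HR − 1.96), with d the number of events. At HR 2.0: d = 48 gives Φ(2.401 − 1.96) = 67%; d = 54 gives Φ(2.547 − 1.96) = 72%; d = 60 gives Φ(2.684 − 1.96) = 77%. The simulated exact-time power agrees.

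**3. Simulation on nominal visit days**, all subjects in the risk set, HR 2.0, 1,000 trials per row. Cells show median estimated HR and power.

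| Control median | Events / distinct times / largest tie | Exact times | Breslow | Efron | Complementary log-log | Log-rank |
|---|---|---|---|---|---|---|
| 4 d | 53 / 4.8 / 20 | 2.01, 71.2% | 1.60, 32.4% | 1.86, 60.8% | 2.06, 67.0% | 62.2% |
| 7 d | 51 / 5.5 / 18 | 1.96, 66.9% | 1.63, 34.3% | 1.88, 58.5% | 2.04, 63.8% | 60.7% |
| 14 d | 49 / 6.4 / 16 | 2.01, 66.5% | 1.69, 39.3% | 1.92, 60.4% | 2.07, 64.4% | 62.0% |
| 30 d | 47 / 6.7 / 14 | 2.04, 66.1% | 1.75, 45.1% | 1.98, 62.6% | 2.09, 65.3% | 62.6% |

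Breslow loses 21 points (66.1 − 45.1) to 39 points (71.2 − 32.4). Efron on the same data loses about 4 (66.1 − 62.6) to 10 (71.2 − 60.8). Other runs, with control medians of 5 to 20 days, gave the same picture. Across all runs exact-time power spans 66–76% and Efron 59–69%.

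**4. Other effect sizes.** At HR 1.5 Breslow gives 1.32 to 1.39 with 9–13% power, against 27–31% with exact times. With no effect it rejects in 0.5–2.8% of trials, so it errs on the conservative side.

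**5. Actual dates within windows.** The possible study days number 1 + 1 + 3 + 3 + 7 + 7 + 15 = 37. With dates spread over the windows and control medians of 5 to 20 days, Breslow gives about 1.76 to 1.89 and 50–63% power. In the two windowed runs at control medians of 7 and 14 days, Efron gave 1.91 and 1.89 (61% and 56%), and log-rank 62% and 57%.

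**6. Improvers only, as 11.3 literally reads** (20% never improving, control median 4 to 14 days, HR 2.0). Breslow gives 1.57 to 1.61 and 27–31%; Efron 1.83 to 1.87 and 51–55%; exact times 58–62% power.

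**7. Effect on later planning.** Required events scale with 1/(ln HR)². Planning from 1.75 instead of 2.0 multiplies them by (0.693/0.560)² = 1.5; planning from 1.60, by (0.693/0.470)² = 2.2.

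**The case against.** A reader might infer that scoring at seven visits by itself costs a third to a half of the power, that the named software makes this certain, and that a real effect would be missed. The documents support none of the three.

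- **The schedule is not the main cause.** Under Efron the same nominal-day data lose only about 4 to 10 points.
- **Breslow is an assumption.** The plan names only a SAS version. No document states a default or a choice.
- **Seven distinct values is the worst case.** The windows allow up to 37 days, and time is counted in days. The nominal-visit rule in SAP 8.6 is written for summary tables. Actual dates soften the Breslow loss but do not remove it, and they help least where early improvement dominates, since Days 2 and 3 have no window.
- **A real effect need not be missed.** The log-rank test is planned on the same endpoint and is largely spared. All endpoints are called exploratory, none is designated the primary efficacy endpoint, no power is claimed, and p-values are descriptive.
- **Other features can matter more.** If 20% never improve and all stay in the risk set, hazards are no longer proportional. The exact-time hazard ratio is then already 1.32 to 1.33 (power 16–17%), and Breslow moves it only to 1.25 to 1.27 (9–10%). The improvers-only wording is also a separate and larger problem.

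These points limit the size and the consequence. The omission remains: the SAP makes the Cox hazard ratio the primary analysis, the log-rank test is unadjusted and yields no hazard ratio, and the value reported depends on an option the SAP does not fix.

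**Conclusion.** The concern holds as a gap in specification with a conditional cost. If Breslow ties are used, a true hazard ratio of 2.0 is estimated at about 1.6 to 1.75 with 32–45% power on nominal visit days, or about 1.76 to 1.89 with 50–63% on actual dates, against about 2.0 and 66–76% with exact times. Efron on nominal days gives about 1.86 to 1.98 and 59–69%, so most of the loss belongs to the tie approximation. Because the log-rank test keeps about 61–63% on nominal days and p-values are descriptive, the main harm is an understated hazard ratio and a conservative Cox p-value that could disagree with the log-rank result.

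These figures assume 30 per arm, proportional hazards, control medians in the ranges shown, no covariate adjustment and all subjects in the risk set. If Efron were in fact used, the cost would be small and the point would reduce to documentation.

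**What to change.** In SAP 11.3:

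1. Specify a proportional hazards model suited to visit data: a grouped-time model (complementary log-log link, one term per visit interval) or an interval-censored model. At minimum, keep Cox and name Efron ties. The discrete tie option is not a like-for-like substitute, because it estimates an odds ratio (2.3 to 2.5 at a true hazard ratio of 2.0 in the improvers-only runs).
2. State that improvement is dated by the actual assessment date.
3. Replace the improvers-only wording so that all mITT subjects stay in the risk set, and state how those who never improve are handled.

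The cost is a few lines in the SAP and a program option, settled before unblinding. No new data are needed. The complementary log-log model recovers hazard ratios of 2.04 to 2.09 and 64–67% power in the nominal-day runs.
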